9.2 Patient demographics and other baseline characteristics

All data for background and demographic variables will be listed by study part and patient. For these parameters summary statistics will be provided accordingly.

Relevant medical history, current medical conditions, results of laboratory screens, drug tests and any other relevant information will be listed by study part and patient.

9.3 Treatments (study drug, rescue medication, other concomitant therapies, compliance)

Study drug, other concomitant therapies, and compliance will be listed by study part and patient.

9.4 Analysis of the primary variable

9.4.1 Variable(s)

Part A:

The tumor size (volume) as assessed by MRI technique up to and including week 4 will be the primary measure of efficacy. The tumor size at baseline and at week 4 will be log transformed. The log ratio to baseline of the tumor size (change from baseline of log transformed volume) will be the primary endpoint.

Part B:

The tumor volume will continue to be the primary measure of efficacy. In particular, if the tumor is too small to be measurable at follow-up, it is considered as complete response.

Part C:

The tumor volume will continue to be the primary measure of efficacy. In particular, if the tumor is too small to be measurable by MRI, it is considered as complete response.

Tumor volumes will be listed and descriptively summarized at each MRI assessment time by MCS110 dose group (3 mg/kg, 5 mg/kg, 10 mg/kg). Moreover, the number and percentage of patients with complete tumor response (CR) will be presented, and the time that the complete tumor response is observed will be listed by patient and dose group. In addition, incidences of patients with partial response (PR), stable disease (SD) and progressive disease (PD) will be listed by dose group.

Tumor volume reduction after 3 doses, evaluated by week 12 MRI, will guide the decision on whether to continue with the initial dosing (3 mg/kg or 5 mg/kg) or increase the dose to 10 mg/kg for the following doses.

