Tumor volumes will be listed and descriptively summarized at each MRI assessment time by treatment groups (treatment group 1 = MCS110 throughout the trial, treatment group 2 = Placebo for the first dose and MCS110 from the second dose) accordingly. Moreover, the number and percentage of patients with complete tumor response will be presented, and the time that the complete tumor response is observed will be listed by patient and treatment group.

In addition, we may pool treatment groups by matching the 1st dose of MCS110 in treatment group 1 to the 2nd dose (1st of MCS110) in treatment group 2. More specifically, for treatment group 2, the measurement right before patients receiving the first dose of MCS110 (2nd dose from screening) will be treated as the new baseline and assessment time-points will be adjusted accordingly.

Part C

The tumor volume will continue to be the primary measure of efficacy. In particular, if the tumor is too small to be measurable, it is considered as complete response.

Tumor volumes will be listed and descriptively summarized at each MRI assessment time by MCS110 dose group (3 mg/kg, 5 mg/kg, and 10 mg/kg). Moreover, the number and percentage of patients with complete tumor response (CR), partial response (PR), stable disease (SD), and progressive disease (PD) based on RECIST criteria will be presented, and the time that the complete tumor response is observed will be listed by patient and dose group.

Tumor volume reduction after 3 doses will guide the decision on whether to continue the lower dose levels of 3 or 5 mg/kg MCS110 with the initial dosing (3 mg/kg or 5 mg/kg) or increase the dosing to 10 mg/kg for the 3 following doses. The decision criteria for the 10 mg/kg arm will remain the same as in Part B.

If a lower dose (3 mg/kg or 5 mg/kg) is well tolerated and shows the same efficacy as 10 mg/kg defined as a tumor volume reduction of at least 45%, evaluated by week 12 MRI after patient received 3 MCS110 doses, then three additional MCS110 doses of the same dose will be administered to the patient. Additional patients may be enrolled in this lower dose group in open label to extend the efficacious arm up to approximately 10 patients.

Assessment Schedule (Part A)

	Screening	Baseline						Tre	eatri	nent						EoS
Visit Numbers		2			3			Т	4	5	6	7	8	9	10	777
Wee	-				1			+	2	4	5	6	8	12	18	24
Study [au - 28 to - 8	-7 to -1			1			+	15	28	33	43	57	85	127	169
Time	-		pre	0	1	2	3 !	_			-			-	-	-

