6.4 Efficacy / Pharmacodynamic assessments

6.4.1 Tumor Volume by MRI

Collection and processing

MRI of the joints with PVNS will be taken during the screening phase. MRI scans have to be scheduled so, that a validated reference MRI should be available within 8 days before patient dosing (Part A and B).

For Part C, a validated reference MRI should be available within 3 weeks before patient randomization. This will allow for the evaluation of the image quality and measurability of tumor sizes. For screening and follow up MRI radiologists should schedule two appointments with the patient with a window of two days to account for a potential rescan.

If this MRI is not validated, a second MRI should be planned to get a validated reference MRI during screening period.

At visits including treatment administration, MRI should be scheduled within 5 days before MCS110 dosing day.

In Part C, at week 12, dose decision point, the MRI should be planned in a sufficient time before dosing day (at least 5 working days) to allow tumor volume evaluation and decision making on potential dose escalation.

Confidential

All MRI scans will be transferred to the Imaging CRO (ICRO) electronically to determine if the images are of good quality without artifacts and to be reviewed by a central radiologist to confirm that the patient has at least one target lesion of measurable tumor size at screening, with minimum lesion dimension of at least 4 times the slice thickness and no less than 10 mm in the longest axis. If the images are not of good quality and/or not measurable, the ICRO will inform Novartis and the clinical sites within 48 hours and will request a new scan. If acceptable, the ICRO will also inform Novartis and the clinical sites and this will be considered as the validated reference MRI. The MRI image is read by two independent readers, for all scans at all timepoints. The RECIST value for the Overall Best Response is taken as the value provided by the first reader. If the values between two readers do not match for overall best response this should be queried by data management and the readers should meet to reach consensus. In addition readers should meet to reach consensus if there is discrepancy in the number of lesions observed.

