7.1 Data post-surgery will not be used for primary analysis - Primary Endpoint

Part A, B and C pooled for weeks 1 to 4 (referred as 'Part A*' hereafter)

The tumor size (volume) as assessed by MRI technique up to and including week 4 will be the primary measure of efficacy. This data will be listed as collected.

Consolidated tumor volume will be calculated as the geometric mean from two readers. Summary statistics of the consolidated tumor volume will be presented by treatment and visit time. The tumor volume measured at screening is treated as baseline. The percent change and absolute change from baseline of the consolidated tumor volume will be summarized in the same fashion. Waterfall plot on percent change from baseline after 4 weeks will be produced. The tumor size at baseline and after 4 weeks will be log transformed. The log ratio to baseline of the tumor size (change from baseline of log transformed volume) will be the primary measure of efficacy for the single dosing part of the study (Part A*).

The analysis of the primary endpoint will quantify the accumulation of evidence about the treatment effect as patients complete their 4 week treatment. The evidence will be summarized in the posterior distributions of the treatment group means and their differences. These posterior distributions will be updated after certain patients complete the 4 week treatment.

For the analysis, the distributional model for the observed data (log ratio) will be the normal model with unknown parameters μ and σ , with μ being the parameter of primary interest (treatment mean) and σ representing the sampling error. This model will be applied to each MCS110 dose group separately. Little prior information is available for these parameters and therefore non-informative prior distributions will be placed on them. For μ a normal prior distribution centered at 0 (no treatment effect) will be used with large standard deviation, and for σ a uniform (0,2) prior distribution.

The model is formally described below, LR being the log ratio of tumor volume:

Likelihood

$$LR_i \sim N(\mu, \sigma)$$

with

$$\mu = \mu_p \text{ for observations from placebo group}$$

$$\mu = \mu_m \text{ for observations from MCS110 group}$$

Prior distributions on treatment means μ 's

$$\mu_p \sim N(0, 0.3)$$

$$\mu_m \sim N(0, 10) \text{ * i.e. Neutral prior or}$$

$$\mu_m \sim N(0, 0.3) \text{ * i.e. Skeptical prior}$$

Prior distributions on sigma

$$\sigma \sim \text{Uniform}(0,2)$$

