The same model as above will also be applied to compare the efficacy of the 3 mg/kg and 5 mg/kg to the 10 mg/kg dose (instead of Placebo).

Part B and C (referenced as Part B* hereafter)

Part B includes all data from multiple dosing Parts. In Part B, treatment group 1 = MCS110 throughout the trial, treatment group 2 = Placebo for the first dose and MCS110 from the second dose. In Part C, treatment arm 1 = MCS110 3 mg/kg, treatment arm 2 = MCS110 5 mg/kg, treatment arm 3 = MCS110 10 mg/kg, for patients in treatment arms 1 and 2 that switch to 10 mg/kg after 3 doses, they will be included in their original treatment group for the first 3 doses and will added in a separate group after that (4= MCS110 3 mg/kg for 3 doses and 10 mg/kg afterwards and 5= MCS110 5 mg/kg for 3 doses and 10 mg/kg afterwards), no re-calculation of baseline will occur for the people who change treatments.

Tumor volumes will be listed at each MRI assessment timepoint till the end of the study by treatment groups.

Part B*: MCS110 data only, by including data starting from the 1st dose of MCS110 in all treatment groups of Parts B and C. More specifically, for Part B treatment group 2, the measurement right before patients receiving the first dose of MCS110 (2nd dose from screening) will be treated as the new baseline and assessment time-points will be adjusted accordingly. Summary statistics of the consolidated tumor volume for the raw values, percent change and absolute change from baseline.

Arithmetic mean (+/-) SE on percent change from baseline vs time plot will be produced for Part B*. Waterfall plot of the maximum reduction until 8 Weeks after last dose will be produced in regards of number of doses received.

Overall Time to complete tumor ablation will be summarised up to the primary endpoint (8 weeks after the last MCS110 dose), along with a summary of overall time to $\geq 50\%$, and $\geq 80\%$ ablation. The number and frequency of patients reaching each level will also be included in the summary.

Overall Time to complete ablation is the time (in weeks) - from first MCS110 dose to the first time when there is no tumor detected. Overall time to $\geq 50\%$, and $\geq 80\%$ ablation is the time from first MCS110 dose to reach maximum ablation of [50%, 80%) and [80%, complete) respectively.

Part C

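### Tumour that is visible but not measurable is a complete response in the protocol and not complete ablation in the SAP, and one reader's zero sets the two-reader volume to zero

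*Protocol*

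**What the plan says.** **Protocol.** Section 9.4.1 makes tumour volume the main efficacy measure in Parts B and C and adds a rule for complete response. For Part B, "if the tumor is too small to be measurable at follow-up, it is considered as complete response". For Part C, "if the tumor is too small to be measurable by MRI, it is considered as complete response". The synopsis repeats the rule for both parts. For Part C the synopsis also names a second basis for the response categories: the counts of complete response through "progressive disease (PD) based on RECIST criteria will be presented".

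Section 6.4.1 gives a numeric limit for measurability in the sentence on confirming a target lesion at screening: "with minimum lesion dimension of at least 4 times the slice thickness and no less than 10 mm in the longest axis". It also provides that two independent readers read every scan, that best overall response comes from the first reader, and that the readers confer if they differ on best overall response or on how many lesions they see.

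**SAP.** The visible text of section 7.1 does not define complete response. Time to complete ablation runs "from first MCS110 dose to the first time when there is no tumor detected". The partial levels are defined as the time "to reach maximum ablation of [50%, 80%) and [80%, complete) respectively", so the upper one stops short of complete. On volume: "Consolidated tumor volume will be calculated as the geometric mean from two readers". Section 7.1.1 leaves missing values missing.

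**The concern.** Not measurable and not detected are different states of the same scan. A small remnant that both readers see but neither can measure is in the first state and not the second. The protocol credits it as a complete response, and the SAP does not credit it as complete ablation. Anyone comparing the response table with the ablation summary could find different patients counted as complete, with nothing in the plan to say which count is right.

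The purpose of Part B makes this distinction matter. Protocol 1.4 asks whether repeated dosing can ablate the tumour completely and so stand as an alternative to surgery. Crediting visible residual tumour as complete leans the answer towards the drug.

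The second issue is arithmetic. A geometric mean of two readings ignores the larger reading once the other is zero. A scan on which the readers disagree about whether anything can be measured would enter the volume summaries as a 100% reduction, unless something intervenes first.

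**Working it through.** **1. The plan's own figure.** Table 9-2 in Protocol 9.13 gives 95% intervals for the complete-response proportion with n = 12. Exact Clopper-Pearson limits, two-sided, reproduce the rows from 1/12 to 11/12 to the printed rounding. For 1/12:

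- lower limit: 1 − 0.975^(1/12) = 0.0021
- upper limit: 0.3848 (printed: 0.002, 0.38)

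The 0/12 upper limit is printed as 0.22. The two-sided value is 1 − 0.025^(1/12) = 0.2646, and the printed figure matches the one-sided bound 1 − 0.05^(1/12) = 0.2209. The 12/12 row behaves the same way (0.7354 two-sided, 0.7791 one-sided). I use two-sided limits below.

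**2. The definitions side by side.** Four states of one follow-up scan:

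| Readers | Protocol 9.4.1 | SAP 7.1 ablation | Consensus under Protocol 6.4.1 |
|---|---|---|---|
| Both detect nothing | Complete response | Complete | Not needed |
| Both detect, neither can measure | Complete response | Not complete | Not triggered, as they agree |
| One detects nothing, one sees a lesion | Depends on reader | Depends on reader | Triggered by lesion count |
| Both detect, only one can measure | Depends on reader | Not complete | Only if best overall response differs |

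The second row is the definitional conflict. It needs no reader disagreement, so consensus cannot resolve it. Such a remnant also has no clear place in the SAP's levels: it is not complete, and putting it in the level just below complete needs a volume that the plan does not assign.

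**3. The two-reader volume.** With readings v1 and v2, the consolidated volume is √(v1 × v2). If v1 = 0, it is 0 for any v2:

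- readings 0 and 0.1 mL: √(0 × 0.1) = 0
- readings 0 and 1 mL: √(0 × 1) = 0
- readings 0 and 20 mL: √(0 × 20) = 0

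The change from baseline V0 is then 100 × (0 − V0)/V0 = −100%. These pairs are illustrations, since the documents give no reader data. The exposed case is the fourth row when the disagreement is at one time point and leaves lesion count and best overall response unchanged. Section 6.4.1 also does not say that consensus revises the volumes.

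**4. Effect of one patient.**

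- Part B, n = 12: 1/12 = 8.3%. The interval moves from 0/12 (0, 0.265) to 1/12 (0.002, 0.385).
- A Part C arm of 6: 1/6 = 16.7%. The interval moves from 0/6 (0, 0.459) to 1/6 (0.004, 0.641).

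**5. How large a remnant could be.** The documents give no measurability limit for follow-up. Two assumptions yield a figure: that the screening limit carries over, and that the lesion is a sphere of volume π/6 × d³.

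- d = 10 mm: π/6 × 1.0³ = 0.52 mL
- d = 16 mm (4 × the 4 mm maximum slice thickness in 6.4.1): π/6 × 1.6³ = 2.14 mL

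Baseline volumes are not given either. Over an assumed 5 to 100 mL, 0.52 mL is 10.5% down to 0.5% of baseline, and 2.14 mL is 42.9% down to 2.1%.

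**The case against.** The best defence has four parts.

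*The size limit applies to screening only.* This stands. Section 6.4.1 ties it to confirming a target lesion at entry, and follow-up volume is a voxel count inside a drawn boundary, which need not stop at 10 mm. A reader might infer that any tumour under 10 to 16 mm is automatically a complete response. The documents do not say so, and the millilitre figures above are conditional.

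*Consensus already handles reader disagreement.* Largely true. If one reader sees nothing and the other sees a lesion, the counts differ and they must confer. What remains is narrow: a volume disagreement at one time point that changes neither lesion count nor best overall response, plus the silence on whether consensus alters the volumes. It does not touch the case where both readers see an unmeasurable remnant.

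*Nothing says that an unmeasurable lesion is entered as zero, or that ablation time comes from the consolidated volume.* Also true. A reader might infer that one reader's zero is reported as complete ablation. That is possible, not established, because the SAP defines that event by detection. But if the value is not zero it may be missing, and 7.1.1 would then drop a very good responder from the volume summaries. A rule is needed either way.

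*Complete response is descriptive.* The primary outcome in Parts B and C is tumour volume eight weeks after the final dose. This limits the consequence but does not remove the conflict. Parts of the SAP are also redacted and its reference list cites the RECIST guideline, so a definition may exist out of view. The two visible rules would still differ.

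**Conclusion.** The point holds in a limited form. The protocol's complete response and the SAP's complete ablation are different events, and the visible text does not reconcile them with each other or with the RECIST basis named in the synopsis. Followed as written, the protocol credits a visible remnant as complete. The response count can therefore exceed the ablation count. This rests on the wording alone.

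The zero in the geometric mean is certain as arithmetic. Its effect on reported results depends on a zero being entered for an unmeasurable lesion and on the disagreement escaping consensus. Neither can be settled from the documents.

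Two further inferences are not supported. One is that Part B was sized on complete response: Protocol 9.13 states about 12 patients and then shows the precision that number gives, without deriving it. The other is that a false zero is likely to change the week-4 analysis. SAP 7.1 does move to square-root ratios if anyone is a complete responder, but the synopsis reports an average single-dose reduction of 40% (29 to 50%), so a complete response at week 4 is unlikely.

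**What to change.** 1. Use one definition for complete response and complete ablation in Protocol 9.4.1, the synopsis, and the SAP's response tables and time summary: no tumour detected by both readers, or by their consensus. Say how this relates to the RECIST categories named for Part C.
2. Report tumour that is detected but not measurable as residual tumour, on its own line. State what makes a lesion unmeasurable at follow-up and what volume it takes in the analysis.
3. When exactly one reader records zero, send the scan to the existing consensus step before the volumes are combined, and say that the consensus reading is the one used. Keep the geometric mean throughout; switching to another average only for these scans would mix two estimators in one endpoint.

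The cost is wording in two documents and one derivation rule, using a reader step that already exists. SAP 1.2 allows a new version before database lock. The complete-response rate may come out lower, by 8 percentage points for each patient reclassified out of 12.

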9.4.2 Statistical model, hypothesis, and method of analysis

Part A:

The analysis of the primary endpoint will quantify the accumulation of evidence about the treatment effect as patients complete their 4 week treatment. The evidence will be summarized in the posterior distributions of the treatment group means and their differences. These posterior distributions will be updated after each patient completes the 4 week treatment.

Confidential

For the analysis, the distributional model for the observed data (log ratio) will be the normal model with unknown parameters μ and σ , with μ being the parameter of primary interest (treatment mean) and σ representing the sampling error. Little prior information is available for these parameters and therefore non-informative prior distributions will be placed on them. For μ a normal prior distribution centered at 0 (no treatment effect) will be used with large standard deviation, and for σ a uniform (0,2) prior distribution.

The model is formally described below, LR being the log ratio of tumor volume:

Likelihood

 $LR_i \sim N(\mu, \sigma)$

with

 $\mu = \mu_p$ for observations from placebo group

 $\mu = \mu_m$ for observations from MCS110 group

Prior distributions on treatment means µ's

$$\begin{split} \mu_p &\sim N(0, \ 0.3) \\ \mu_m &\sim N(0, \ 10 \) \ * \ i.e., \ Neutral \ prior \ or \\ \mu_m &\sim N(0, \ 0.3) \ * \ i.e., \ Skeptical \ prior \end{split}$$

Prior distributions on sigma

 $\sigma \sim \text{Uniform}(0,2)$

Decision Rule

The PoC criterion is two-fold, as follows:

- 1. Prob(LR(treated) < LR(placebo)) > 0.90; i.e., 90% confidence in superiority to placebo
- 2. Prob(LR(treated) LR(placebo) < log(0.6)) > 0.50; i.e., 50% confidence in the treated group ratio being 40% below the placebo group ratio

At least one placebo patient and two MCS110 patients must be included to declare PoC. Both neutral and skeptical priors will be used to assess the PoC criterion. The skeptical prior is used to shift prior beliefs toward no effect of MCS110, i.e., stronger evidence from the data in favor of MCS110 will be needed to reach PoC. The skeptical analysis will only be run as a sensitivity analysis.

[figure not shown]
Once the PoC criterion is reached, the clinical trial team (CTT) may decide to continue recruitment to collect more data on MCS110.

Novartis	Confidential	Page 129
Amended Protocol Version v07 (Clean)		Protocol No. CMCS110X2201

If after 6 patients have completed the 4 week treatment, the PoC criterion is not reached, the probability to reach PoC with the addition of 6 new patients will be assessed, and if this probability is less than 10% the trial may be stopped for futility.

For illustration, an example of a trial path simulation with skeptical and neutral priors on mean treatment effect in MCS110 group is shown below (Figure 9-1):

Figure 9-1 Example of a sample path

The left plot displays the skeptical analysis and the right plot the neutral analysis.

The blue dots represent the posterior mean in the MCS group and the black dots represent the posterior means in the placebo group as more patients contribute data.

The green dots show the probability of MCS110 being superior to placebo, and the pink dot the probability to be better by 40%.

In this example, the PoC criterion is reached after 3 patients when neutral prior (second graph) is used, and after 4 patients when skeptical prior (first graph) is used.

Part B:

Tumor volumes will be listed and descriptively summarized at each MRI assessment time by treatment groups (treatment group 1 = MCS110 throughout the trial, treatment group 2 = Placebo for the first dose and MCS110 from the second dose) accordingly. Moreover, the number and percentage of patients with complete tumor response will be presented, and the time that the complete tumor response is observed will be listed by patient and treatment group.

In addition, we may pool treatment groups by matching the 1st dose of MCS110 in treatment group 1 to the 2nd dose (1st of MCS110) in treatment group 2. More specifically, for treatment group 2, the measurement right before patients receiving the first dose of MCS110 (2nd dose from screening) will be treated as the new baseline and assessment time-points will be adjusted accordingly. This may apply to all analyses in Section 9 if necessary.

Part C:

Tumor volumes will be listed and descriptively summarized at each MRI assessment time by treatment arm (treatment arm 1 = MCS110 3 mg/kg, treatment arm 2 = MCS110 5 mg/kg, treatment arm 3 = MCS110 10 mg/kg) accordingly. Moreover, the number and percentage of patients with complete tumor response (CR) will be presented, and the time that the complete

tumor response is observed will be listed by patient and treatment arm. In addition, incidences of patients with partial response (PR), stable disease (SD) and progressive disease (PD) will be listed by treatment arm.

Confidential

More specifically, for patients in treatment arms 1 and 2 that switch to 10 mg/kg after 3 doses, the measurement right before patients received the first dose of MCS110 10 mg/kg (4th dose from screening) will be treated as the new baseline and assessment time-points will be adjusted accordingly. This may apply to all analyses in Section 9 if necessary.

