3.2.2 Study design Part C

The study CMCS110X2201 Part C is a randomized, double-blind, parallel-arm adaptive dose exploration study part. Approximately 15 patients, including adults and adolescents (>12 years old), will be randomized to receive 3 mg/kg, 5 mg/kg or 10 mg/kg MCS110 in a ratio of approximately 2:2:1 and a potential further extension of the efficient lower dose arm. Tumor volume reduction after 3 doses, assessed by MRI at week 12, will guide the decision on whether to continue with the initial dosing (3 mg/kg or 5mg/kg) or increase for the following three doses to 10 mg/kg to allow the patient to benefit from the drug.

The adult patients will follow Assessment schedule Part C.

The adolescent patients will follow Assessment Schedule Part C-Adolescent patients, adapted to reduce the required blood volume to maximum 25 mL per time point and 50 mL in 8 weeks (Howie 2011).

Conditions of dose level change after 3 doses

Patients enrolled in 3 mg/kg and 5 mg/kg arms: 3 additional MCS110 doses of the same dose will be administered, if MCS110 is well tolerated and if a reduction in tumor volume of >45%can be demonstrated after the 3rd MCS110 dose evaluated by MRI taken just before the 4th dose. This MRI is reflecting potential efficacy of 3 doses. If the drug is well tolerated and the tumor volume reduction is <45%, then three additional MCS110 doses of 10 mg/kg will be administered.

Process of dosing after 3 doses

All patients within each arm will receive 3 doses of the same initial dose at Day 1, week 4 and week 8.

At week 12, an MRI and safety examinations will be taken before the planned 4th dose. The unblinded statistician(s) and an unblinded Novartis medical person (unblinded safety reviewer) will review the tumor volume reduction data from baseline to week 12 MRI and patient's safety data. The unblinded safety reviewer will inform the site's unblinded pharmacist on the dose level to administer at week 12:

- Patients enrolled in 3 mg/kg and 5 mg/kg arms can receive same initial dose or increase to 10 mg/kg.
- Patients enrolled in 10 mg/kg arm: can either stop after 4 doses or receive up to 6 doses of 10 mg/kg under conditions described in the Section 5.5.5.2 (Dosing extension to 6) consecutive doses once every 4 weeks).

Corporate Confidential Information

The primary outcome of Part C of the study will be the tumor volume after multiple doses of MCS110 determined by MRI which will be assessed 8 weeks after the last dose of MCS110.

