- Part C (arm 10mg/kg): the tumor response to treatment is <45 % of tumor volume reduction after the 3rd dose [determined by MRI at week 12] and MCS110 was tolerated: the patient can receive 1 additional dose of 10 mg/kg

New treatment course in case of recurrence of tumor or regrowth of residual tissue

If, based on MRI, relapse is identified, it is possible to start an additional course of 6 consecutive doses of MCS110 10 mg/kg, if there was:

- Good tolerability of MCS110 during the first treatment cycle
 - Patient received 6 doses
 - No early treatment discontinuation

- Good response in tumor volume reduction: Tumor volume reduction at (up to) 1°EP (8 wks post last dose of 6 doses) of >50% during the 1st treatment cycle
- Relapse defined as:
 - Symptoms (pain, swelling, redness, stiffness) and
 - Tumor volume increase greater than 50% of the difference between tumor volume at BL and the lowest tumor volume measured by MRI.
- Last dose of MCS110 was at least \geq 6 months ago.
- Inclusion/exclusion criteria are still fulfilled.

During the second treatment course safety monitoring will be the same as during the first treatment course. Efficacy will be assessed by MRI after the 3rd dose at week 12 to decide on dosing beyond 4 doses and then again 8 weeks post last dose. Once a lower dose with same efficacy as 10 mg/kg has been identified in Part C, relapse patients will receive the lower dose treatment. During the second treatment course no placebo dose will be administered.

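### For Part C patients escalated to 10 mg/kg, the protocol resets baseline to the week-12 MRI and the SAP forbids this, so baseline-relative tumour-volume results after the switch depend on which document is followed.

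*Protocol*

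**What the plan says.** Protocol 9.4.2, Part C, covers patients in the 3 and 5 mg/kg arms who move to 10 mg/kg after three doses. It states that "the measurement right before patients received the first dose of MCS110 10 mg/kg (4th dose from screening) will be treated as the new baseline" and that their assessment times shift accordingly. It then adds: "This may apply to all analyses in Section 9 if necessary".

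SAP 7.1, under the heading for Parts B and C, covers the same patients. It places them in separate groups after the switch and states that "no re-calculation of baseline will occur for the people who change treatments". The SAP's general definition, given under its weeks 1 to 4 heading, is "The tumor volume measured at screening is treated as baseline". The SAP's Part C text adds no reset.

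The scan in question is fixed by Protocol 3.2.2: "At week 12, an MRI and safety examinations will be taken before the planned 4th dose". The same scan decides who switches. If the drug is well tolerated and the "tumor volume reduction is <45%, then three additional MCS110 doses of 10 mg/kg will be administered".

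Both documents also reset baseline for Part B patients whose first dose was placebo, and there they agree. The conflict is confined to Part C switchers.

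**The concern.** The two documents give opposite instructions for the reference value of the same patients, and the text of the SAP that can be read does not acknowledge the departure. Whoever produces or reads the tables has two pre-written baselines to choose from.

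The protocol's rule is also the weaker one for Part C, for three reasons.

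- **It removes drug effect.** The Part C primary objective is the effect of multiple doses, judged 8 weeks after the last one. A week-12 baseline drops whatever the first three doses achieved. The Part B reset does not have this flaw, because there the new baseline is the last scan before any MCS110.
- **It uses the selecting scan as the reference.** Switchers are chosen because their week-12 volume was too high. Part of that height is measurement error, so change measured from that scan will tend to overstate the benefit after escalation.
- **It moves the clock.** The primary scan at week 28 would become week 16 (28 − 12), so switchers and non-switchers would no longer share a time axis.

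At stake are the percent-change and absolute-change summaries and plots after week 12, and the modelled log ratios that use post-switch scans. In arms of about 6, a few switchers can move a mean visibly.

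**Working it through.** The plan gives no figure of its own to reproduce here, so the check is direct arithmetic on the two rules.

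**Inputs**
- V0, V12, Vf: tumour volume at screening, at week 12 and at the primary MRI.
- r1 = 1 − V12/V0, the reduction to week 12. It is below 45% in any switcher (Protocol 3.2.2). It can be negative.
- r2 = 1 − Vf/V12, the further reduction after week 12. The documents do not give it. Assumed range: 0% to 50%. The upper end is the average reduction of about 50% after three 10 mg/kg doses in Part B (Protocol 1.4).
- Patients who could switch: about 6 in each lower-dose arm in the double-blind phase (Protocol Table 5-1), so at most about 6 + 6 = 12. No expected switching rate is given.

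**Formulas**
- Percent reduction: the SAP rule gives 1 − (1 − r1)(1 − r2); the protocol rule gives r2. Gap = r1(1 − r2).
- Absolute reduction: V0 − Vf against V12 − Vf. Gap = V0 − V12 = r1·V0.
- Log ratio: the SAP value minus the protocol value is log(1 − r1), whatever r2 is.
- Time from baseline: 12 weeks apart.

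**Results for percent reduction**

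| r1 | r2 | SAP rule | Protocol rule | Gap (points) |
|---|---|---|---|---|
| 44% | 0% | 44.0% | 0.0% | 44.0 |
| 44% | 30% | 60.8% | 30.0% | 30.8 |
| 44% | 40% | 66.4% | 40.0% | 26.4 |
| 44% | 50% | 72.0% | 50.0% | 22.0 |
| 30% | 30% | 51.0% | 30.0% | 21.0 |
| 30% | 50% | 65.0% | 50.0% | 15.0 |
| 20% | 50% | 60.0% | 50.0% | 10.0 |
| 10% | 50% | 55.0% | 50.0% | 5.0 |
| −10% | 40% | 34.0% | 40.0% | −6.0 |

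For example, at r1 = 44% and r2 = 50%, the SAP rule gives 1 − 0.56 × 0.50 = 0.72.

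The percent gap is zero if r1 = 0 or if the tumour has gone (r2 = 100%). Because r1 is below 45%, it stays below 45 × 0.70 = 31.5 points at r2 = 30%, and below 45 × 0.50 = 22.5 points at r2 = 50%. A gap of 20 points needs r1 of at least 20/0.70 = 28.6% or 20/0.50 = 40%, respectively.

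On the log scale the shift is log(0.56) = −0.58 at r1 = 44% and log(0.90) = −0.105 at r1 = 10%.

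**One patient, with assumed volumes.** Screening 100 mL, week 12 65 mL (35% reduction, so escalated if the drug was tolerated), primary MRI 45 mL. The SAP rule gives 1 − 45/100 = 55%. The protocol rule gives 1 − 45/65 = 31%. The absolute reductions are 55 mL and 20 mL. The two percentages fall on either side of the 50% ablation level that SAP 7.1 tabulates. The 45 mL itself is the same under both rules.

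**The case against.** The best reply is that the SAP already settles the matter. It is the document that guides programming, it names these patients, and it forbids recalculation. The protocol paragraph looks like carry-over from Part B: it opens as if elaborating an earlier statement that Part C does not contain, its extension to other analyses applies only if needed, and the synopsis gives no reset for Part C. Parts of the SAP's opening sections are redacted, so an explanation may exist that cannot be seen.

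This lowers the practical risk, and it is fair to call the repair an edit. It does not remove the conflict. The baseline sentence in the current protocol is unconditional, and the optional wording concerns only wider use.

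Four stronger readings are tempting and are not supported.

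- **That the primary outcome itself changes.** Protocol 3.2.2 says: "The primary outcome of Part C of the study will be the tumor volume after multiple doses of MCS110 determined by MRI". That volume is the same under either rule, and 9.4.2 summarises it descriptively. No Part C test at that time point depends on the baseline choice.
- **That the lower-dose question turns on this.** The dose decision uses change from baseline to week 12, and Protocol 3.2.3.2 places the simulation behind the >80% power statement at week 12. Both precede any switch.
- **That the relapse threshold moves.** The definition, "Tumor volume increase greater than 50% of the difference between tumor volume at BL and the lowest tumor volume measured by MRI", is a condition for re-treatment in Protocol 5.5.5.2 and also requires symptoms. The reset reaches at most Section 9, and the relapse text there (9.5.1) sets no threshold.
- **That RECIST categories change.** Best overall response comes from the MRI readers (Protocol 6.4.1). Nothing shows that the reset reaches it.

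It is also true that no text says a switcher contributes two week-4 values to one analysis, and that the regression to the mean is not quantified here.

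**Conclusion.** The contradiction is real, but its reach is limited. It affects Part C switchers after week 12, and only measures taken relative to baseline: percent change, absolute change, log ratio and time from baseline.

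The percent-reduction gap runs from nothing to more than 20 points within the protocol's own switching rule. It is largest for patients who just missed the 45% mark and small for those who had barely responded. These sizes rest on assumed values of r2, because no post-switch response is stated. The effect on a group mean cannot be given, because the number of switchers is unknown beyond the ceiling of about 12 in the double-blind phase.

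The SAP's rule fits the multiple-dose objective and the protocol's does not.

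**What to change.** Amend the Part C paragraph of Protocol 9.4.2 to match SAP 7.1. For patients who switch, keep the screening MRI as baseline and count time from the first MCS110 dose in all Part C baseline-relative tumour-volume analyses. State the same rule once under the SAP's own Part C text, since it now appears only under the combined heading for Parts B and C.

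If change since escalation is of interest, show it as a separate descriptive table, labelled as change from week 12 in escalated patients only, with a note that the baseline scan is also the one that selected them.

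The cost is about a paragraph of wording. No new data or scans are needed, and no dosing rule changes.
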